8.6.3 Hypothesis Testing Strategy

Testing of the primary efficacy endpoint will be 2-sided and conducted at the 5% error level. The study will be considered positive if the null hypothesis of no treatment difference is rejected in favor of the alternative that patients randomized to CR845 experience significantly less itching as measured by the change from baseline to Week 12 of the Treatment Period with respect to the weekly mean of the 24-hour Worst Itching

Intensity NRS score. This is a Phase 2 study designed to identify a safe and efficacious dose; therefore, each CR845 dose group will be compared against placebo. There will be no adjustment for multiple comparison.

8.6.4 Additional Efficacy Endpoints

8.6.4.1 Itch-intensity Measures

Itch-intensity measures and their analyses will include:

- Proportion of patients who have an improvement from baseline at Week 12 of the Treatment Period with respect to the weekly mean of the 24-hour Worst Itching Intensity NRS scores ≥ 1 , ≥ 2 , and ≥ 4 points. The calculation of the proportions will be based on the NRS data using an MI approach for the missing data as in the primary efficacy analysis. Treatment differences will be compared using a logistic regression model with terms for treatment group, baseline NRS score and renal disease status.
- A figure presenting the proportion of patients who have an improvement from baseline in NRS scores at Week 12 that are ≥ 1 , ≥ 2 , ≥ 3 , and ≥ 4 will be prepared.
- Change from baseline in the weekly mean of the 24-hour Worst Itching Intensity NRS score at each week of the Treatment Period (Week 1 to Week 12). Treatment differences between CR845 and placebo at each postbaseline time point will be evaluated using the same MMRM detailed in [Section 8.6.1](#).
- Proportion of patients who rate their itch condition as “Very much improved” or “Much improved” at the end of Week 12 of the Treatment Period/end of treatment, as measured by the PGIC. Treatment difference will be tested using the Cochran-Mantel-Haenszel test, adjusting for strata. An exact test, such as the Fisher’s exact test, may be used if the observed count in a particular cell is small (ie, <5).
- The number and percentage of patients in each of the 5 categories of the Patient Global Impression of Worst Itch Severity at baseline and at each week of the Treatment Period will be tabulated. In addition, the proportion of patients who have a 1-point improvement or more at each week of the Treatment Period, as measured by the Patient Global Impression of Worst Itch Severity. Pairwise treatment differences with respect to this variable will be tested using the Fisher’s exact test.

8.6.4.2 Itch-related Quality-of-Life Measures

Itch-related quality-of-life measures and their analyses will include:

- Change from baseline in itch-related quality of life at each week of the Treatment Period, as assessed by the total score of the 5-D Itch Scale. Treatment differences

between each CR845 dose group and placebo at each postbaseline time point will be evaluated using the same MMRM fitted for the secondary efficacy analysis.

- Change from baseline in itch-related quality-of-life at each week of the Treatment Period, as assessed by the total score of the Skindex-10 Scale. Treatment differences between each CR845 dose group and placebo at each postbaseline time point will be evaluated using the same MMRM fitted for the secondary efficacy analysis.
- Change from baseline in itch-related quality of life at Week 12 of the Treatment Period and at each of the remaining weeks of the Treatment Period with respect to each of the 3 domains of the Skindex-10 Scale. Treatment differences with respect to each domain will be evaluated using a model similar to the MMRM fitted for the analysis of the change from baseline in the total score of the Skindex-10 Scale.
- Change from baseline in itch-related quality of life at Week 12 of the Treatment Period and at each of the remaining weeks of the Treatment Period with respect to each of the domains of 5-D Itch Scale. Treatment differences with respect to each domain will be evaluated using a model similar to the MMRM fitted for the analysis of the change from baseline in the total score of the 5-D Scale.

8.7 Safety Analyses

Analysis of all safety data will be performed using the Safety Population. Safety data will be summarized descriptively. No inferential statistics are planned. The baseline value for all analyses of safety parameters will be defined as the last value obtained prior to the first dose of study drug and will include both scheduled and repeat (unscheduled) observations.

8.7.1 Exposure to Study Drug and Compliance

For this study, the duration of treatment for each individual patient may be up to 12 weeks, for a total of 84 doses of study drug. Day 1 of the Treatment Period will be defined as the day of administration of the first dose of study drug. The last day of the Treatment Period will be defined as the day of the last dose taken by the patient (determined based on the patient daily dosing diary). For all patients, the last day of study will be defined as the date of the Follow-up Visit.

Exposure and treatment compliance during the Treatment Period will be summarized by the following parameters:

- Duration of treatment (days)
- Duration of study (days)

- Total number of doses received (based on the patient daily dosing diary)
- Total number of missed doses (0, 1, ≥ 2) (based on the patient daily dosing diary)
- Percent compliance (<80%, 80% to 110%, >110%). Compliance will be calculated in 2 different ways: based on the patient daily dosing diary and using drug accountability records

8.7.2 Adverse Events

All adverse events will be coded using MedDRA dictionary to the corresponding MedDRA SOC and Preferred Term for standardization and summary purposes.

All reported adverse events (whether or not treatment-emergent) will be included in a by-patient adverse event listing. Only TEAEs will be included in summary tables.

Adverse events that are considered “treatment emergent” relative to the Run-in Period are identified as any adverse event with an onset date after the start of the Run-in Period and up to the first dose of study drug during the Treatment Period.

Adverse events that are considered “treatment emergent” relative to the Treatment Period are identified as any adverse event with an onset date after the first dose of the study drug up to the study End of Treatment/Early Termination Visit (or 7 to 10 days after the last dose if no End of Treatment/Early Termination Visit was conducted), whichever is later.

Treatment-emergent adverse events will be summarized by treatment group and by period (Run-in Period vs Treatment Period). The incidence of TEAEs will be presented using counts and percentages of patients with adverse events and tabulated by SOC and Preferred Term. System Organ Class will be sorted alphabetically and Preferred Term within SOC will be sorted by descending frequency based on the incidence across patients overall. A patient will be counted only once in the incidence count for a MedDRA SOC or Preferred Term, although a patient may have multiple occurrences (start and stop) of an event associated with a specific MedDRA Preferred Term or SOC.

The following specific summary tables will be generated:

- Incidence of TEAEs
- Incidence of TEAEs related to study drug
 - If the relationship to the study drug of an adverse event is missing, a worst-case scenario will be assumed (ie, the adverse event will be categorized as “related” to the study drug). If a patient reports 2 or more adverse events that code to the same Preferred Term, the event with the maximum relationship will be included in the table.
- Incidence of TEAEs by maximum severity

- If the severity to the study drug of an adverse event is missing, a worst-case scenario will be assumed (ie, the adverse event will be categorized as “severe”). If a patient reports 2 or more adverse events that code to the same Preferred Term, the event with the maximum severity will be included in the table.
- Incidence of TEAEs occurring in $\geq 5\%$ of patients in at least 1 treatment group
- Incidence of treatment-related TEAEs occurring in $\geq 5\%$ of patients in at least 1 treatment group
- Incidence of serious TEAEs
- Incidence of TEAEs leading to study drug discontinuation

In addition, an overall summary table will be provided, presenting for each treatment group: the number and percentage of patients with an adverse event (both treatment and non-treatment emergent), a TEAE, serious TEAE, related TEAE, severe TEAE, TEAE leading to dose interruption, and TEAE leading to study drug discontinuation. This table will also include the number of events.

All adverse events will be listed in chronological order, including patient identifier, age, race, gender, a flag indicating whether the event was treatment-emergent, and all related event status information (start and stop dates, whether the event was ongoing, study day of onset, severity, seriousness, relationship to study drug, action taken with study drug, and outcome). Separate listings will be generated for SAEs, deaths, and adverse events leading to study drug discontinuation. Additionally, a coding list of Preferred Terms and the verbatim text associated with them will be produced.

8.7.3 Clinical Laboratory Evaluations

Summary statistics for each scheduled time point measured and mean changes from baseline to each time point (when applicable) will be presented for clinical laboratory results.

All laboratory evaluation summaries will include the patients in the Safety Population who have at least 1 postbaseline time point (for criteria based on postbaseline assessments) and with both a baseline and at least 1 postbaseline time point (for criteria evaluating changes from baseline).

Laboratory values will be reported in Système International units.

Laboratory test results will be assigned an L/N/H classification according to whether the value was below (L), within (N), or above (H) the laboratory parameter’s reference range. Comparisons will be based on 3×3 tables (shift tables) that, for a particular laboratory test, compare the baseline L/N/H classification to the highest and/or lowest L/N/H classification during the treatment period. Clinically important laboratory values based on prespecified criteria defined in the SAP will also be summarized.

Additionally, alanine aminotransferase, aspartate aminotransferase, bilirubin, and alkaline phosphatase will be presented in a separate listing, with $3 \times$ and $5 \times$ ULN flagged for alanine aminotransferase and aspartate aminotransferase; $2 \times$ ULN flagged for bilirubin, and $1.5 \times$ ULN flagged for alkaline phosphatase.

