- e. Training on Skindex-10, 5-D Itch, and Patient Global Impression of Worst Itch Severity may be performed at any time during the Run-in Period or on Day 1 of the Treatment Period.
- f. Patients will be requested to complete the NRS worksheets at a similar time each day.
- g. Skindex-10, 5-D Itch, and Patient Global Impression of Worst Itch Severity are to be completed at the clinical site.
- h. Concomitant medications will be updated at each study visit following the first dose of study drug on Day 1.
- j. A phone follow-up will be conducted, unless otherwise necessary.

Table 3. Schedule for Patient-reported Outcome Assessments and Training

Study Week	Visit Days	Run-in Period		Treatment Period				EOT or Early Termination	
		Treatment Period							
				1	4	8	10		
	-7	-6 to -1	1	28	56	70	12	84 (or following discontinuation at any time)	
PRO TRAINING									
Worst Itching Intensity NRS	X			Refresher training, as needed.					
Skindex-10 and 5-D Itch worksheets		Any time during the Run-in Period or Day 1	X	Refresher training, as needed					
PRO ADMINISTRATION/RECORDING									
Worst Itching Intensity NRS	X	Worksheet completed daily ^a	Worksheet completed daily ^a				X		
Skindex-10, 5-D Itch Scale, Patient Global Impression of Worst Itch Severity ^b			X	X	X	X		X	
Patient Global Impression of Change ^b								X	

NRS = numerical rating scale; PRO = patient-reported outcome

a. To be completed at home around a similar time of day.

b. To be completed at the clinical site.

Unscheduled visits may be necessary for outstanding, unresolved adverse events (eg, additional safety laboratory or clinical evaluations). At minimum, for any unscheduled visit, the reason for the visit will be recorded and the adverse event(s) reported, as well as changes to concomitant medications, as applicable. Additional testing (eg, laboratory tests, vital signs, ECGs) will be performed, as clinically indicated.

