8 STATISTICAL METHODS

8.1 General statistical conventions

All statistical procedures will be completed using SAS version 9.2 or higher.

Unless otherwise noted, continuous variables will be summarized using descriptive statistics, including number of patients with non-missing observation (n), mean, median, standard deviation (SD), minimum (min) and maximum (max). Means and medians will be reported to one decimal place more than the raw data. Standard deviation will be reported to two more decimal places than the raw value. The minimum and maximum will be reported to the same decimal as the raw data.

Categorical variables will be summarized using the frequency count and the percentage of patients in each category. All percentages will be rounded to one decimal point. The number and percentage of patients will always be presented in the form XX (XX.X%) where the percentage is in parentheses. To ensure completeness, all summaries for categorical and discrete variables will include all categories, even if none of the patients in a particular category. Counts of zero in any category will be presented as “0”. Unless otherwise noted, for all percentages, the number of patients in the analysis population for the treatment group will be the denominator.

“Baseline” will be defined as per [section 7.1](#). For efficacy endpoints, “on-treatment” is defined as any assessment following the first dose of study drug and within 2 days from the last dose of study drug recorded in the patient diary. For safety endpoints (excluding adverse events), any assessment within 7 days after last dose of study drug will be deemed “on-treatment”. For all endpoints “End of treatment” (EOT), in summaries, will be represented by the last non-missing on-treatment value recorded up to and including the Week 12/Early Termination visit. Treatment emergence for adverse events is described in [section 8.7.1](#). Summaries will be presented across all scheduled visits and EOT unless stated otherwise. Only on-treatment data will be used in summaries and statistical analyses (with the exception of the Patient Global Impression of Change).

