Unless otherwise stated, all statistical testing will be two-sided and will be performed using a significance (alpha) level of 0.05. Two-sided 95% confidence intervals (CI) will be provided appropriately. For tests of hypothesis of treatment group differences, the associated p-value will be reported. All p-values will be rounded to three decimal places; p-values that round to 0.000 will be presented as “< 0.001”.

All patients data, including those derived, will be presented in individual patient data listings. Unless otherwise stated, unscheduled visit results will be included in date/time chronological order, within patient listings only. All listings will be sorted by treatment, patient number, date/time and visit. Patient listings of efficacy and safety data will be presented for all full analysis set and safety set patients respectively unless specified otherwise.

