8.7.2 Clinical laboratory evaluations

Blood samples for clinical laboratory tests, including hematology, serum chemistry and serum pregnancy will be collected during screening and day 1 before study drug administration, on week 6 and week 12 (end of treatment).

All clinical laboratory data will be reported in Système International units.

Summary statistics for each scheduled time point measured and mean changes from baseline to each time point will be presented for hematology and serum chemistry laboratory results. The baseline value is defined as the last observation prior to or on the date of the first dose of study drug whether scheduled or unscheduled (see [section 7.1](#)).

Hematology and serum chemistry laboratory test results will be assigned as Low (L), Normal (N) or High (H) classification according to whether the value was below (L), within (N), or above (H) the laboratory parameter’s reference range.

Statistical Analysis Plan (SAP)

Comparisons will be based on 3×3 tables (shift tables) that, for a particular laboratory test, compare the baseline L/N/H classification to the highest and/or lowest L/N/H classification during the treatment period.

Clinically important laboratory values based on the below specified criteria will also be summarized.

- Alanine aminotransferase (ALT), aspartate aminotransferase (AST),
 - $>3 \times$ ULN
 - $>5 \times$ ULN
 - ALT $>3\times$ ULN or AST $>3\times$ ULN
- Alkaline phosphatase (ALP)
 - $>1.5 \times$ ULN
- Total Bilirubin (TBILI)
 - $>2 \times$ ULN
- AST and Total Bilirubin
 - AST $>3\times$ ULN and TBILI $>2\times$ ULN
- ALT and Total Bilirubin
 - ALT $>3\times$ ULN and TBILI $>2\times$ ULN
- AST or ALT and Total Bilirubin
 - AST or ALT $>3\times$ ULN and TBILI $>2\times$ ULN

A summary of treatment emergent sodium findings will also be provided, categorizing results into those <146 mmol/L, $146 - 150$ mmol/L, and >150 mmol/L at the 6 and 12 week assessments. An additional summary will present these categories for subjects over the full study period presenting the highest category attained (at any on-treatment assessment) and sustained (at any on-treatment assessment and all subsequent on-treatment assessments); this analysis will include both scheduled and unscheduled laboratory test results.

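### The laboratory shift tables and liver-threshold table carry no stated exception to the SAP's listings-only rule for unscheduled results, so peaks on clinically indicated draws will usually be left out of both

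*Protocol*

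**What the plan says.** Three rules in the SAP meet here.

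- **Default for unscheduled results (SAP 8.1).** "Unless otherwise stated, unscheduled visit results will be included in date/time chronological order, within patient listings only". The same section adds: "Summaries will be presented across all scheduled visits and EOT unless stated otherwise".
- **The two laboratory tables (SAP 8.7.2).** The shift tables "compare the baseline L/N/H classification to the highest and/or lowest L/N/H classification during the treatment period" (Protocol 8.7.3 and SAP 8.7.2 use the same words). For the liver criteria (ALT or AST above 3 and 5 times ULN, ALP above 1.5 times, total bilirubin above 2 times, and combinations) the SAP says: "Clinically important laboratory values based on the below specified criteria will also be summarized". Unscheduled draws are mentioned for neither table.
- **Written exceptions.** For the additional sodium summary of highest category attained and sustained, SAP 8.7.2 states that "this analysis will include both scheduled and unscheduled laboratory test results". SAP 8.7.3 has an equivalent sentence for clinically notable vital signs.

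On the conduct side, SAP 8.7.2 schedules on-treatment blood draws at Weeks 6 and 12 only. Protocol 6.5 foresees unscheduled visits for unresolved adverse events: "Additional testing (eg, laboratory tests, vital signs, ECGs) will be performed, as clinically indicated".

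**The concern.** A table of the most extreme class on treatment is useful only if it sees the extreme values. With two scheduled draws in 12 weeks, many of the informative values in a patient with a developing abnormality may come from extra draws prompted by symptoms or by a previous result. The default in SAP 8.1 sends those results to listings.

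The clinically important laboratory values are part of the interim safety output (SAP 8.9.2.5), at an analysis where unsafe or poorly tolerated doses are to be dropped (SAP 8.9). At the end, the study is called positive if at least one safe and efficacious dose is found (SAP 8.6.2). Safety analysis is descriptive (Protocol 8.7), with no formal test behind these counts. A patient who meets the combined transaminase and bilirubin criterion only on an unscheduled draw could be flagged in a listing and still be absent from the count.

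**Working it through.** The documents state no figure to reproduce. The check is a reading of the rules, with a day count for the visit-window rule.

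**1. Does the wording of the two tables amount to an exception?** Compare the four period-wide safety summaries.

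- Sodium, attained and sustained: covers the full study period and any on-treatment assessment; unscheduled results expressly included.
- Notable vital signs: by week and overall for the Treatment Period; unscheduled results expressly included.
- L/N/H shift tables: highest and/or lowest class in the treatment period; nothing stated.
- Liver thresholds: criteria listed only, with no statement whether worst, any or by-visit values count; nothing stated.

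In the first two the authors added the sentence on unscheduled results even beside period-wide wording. Such wording alone was evidently not treated as enough, so the natural reading of the last two is that the SAP 8.1 default applies. The sodium shift table and the attained-sodium summary could then rest on different draws from the same patient.

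**2. Can an unscheduled value enter by another route?**

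- *Visit windows (SAP 7.3, applied to safety endpoints).* An unscheduled value within 2 days of a planned visit is assigned to that visit, but non-missing scheduled and early-termination values take priority, even if lower.
- *End of treatment (SAP 8.1).* This is the last non-missing on-treatment value up to the Week 12 or Early Termination visit. It may occasionally be an unscheduled value, but it is chosen because it is last, not because it is worst.

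**3. Reach of the window rule.** Assume 12 full weeks of dosing. Safety data count as on-treatment up to 7 days after the last dose, so the days after Day 1 are Days 2 to 91: 91 − 2 + 1 = 90 days.

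- Windows around the two laboratory visits: Days 40–44 and 82–86, 5 + 5 = 10 days; 10/90 = 11%. The other 80 days (89%) lie outside.
- If the windows of all six planned visits (Days 14, 28, 42, 56, 70, 84) could be used: 6 × 5 = 30 days; 30/90 = 33%. The other 60 days (67%) lie outside.

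These are shares of calendar days, not of draws or patients. They show only that the window rule is a narrow door.

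**4. Direction.** The highest class over all draws is at least the highest over a subset, and the lowest class is at most the lowest over a subset. A count of patients with any value over a threshold likewise cannot fall when draws are added. Leaving draws out can therefore only lower the number of abnormal patients in an arm. If clinically indicated draws with abnormal results are more frequent on active drug, the difference from placebo shrinks as well.

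**5. Weight of one patient.** At the interim, 50–60% of 240 is 120–144 patients, or 30–36 per arm: one patient is 1/30 = 3.3% to 1/36 = 2.8%. At the end, with 60 per arm, one patient is 1/60 = 1.7%; with 120 per arm, 1/120 = 0.8%. This is the weight of each omitted patient, not an estimate of how many are omitted.

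**The case against.** The best case for the plan has four parts.

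- **The shift-table wording is itself the exception.** A highest or lowest class during the treatment period could be read as otherwise stating the rule. This is possible, but the explicit sentences for sodium and vital signs tell against it. At best the text is ambiguous, and two programmers could produce different tables. Protocol 8.1 gives the SAP primacy where they differ, so the protocol wording does not settle it.
- **Early terminators have a planned draw.** Chemistry and hematology are scheduled at end of treatment or after discontinuation at any time. A patient who stops drug over a liver abnormality is therefore due a planned draw close to the event. This stands and rules out any claim that off-schedule peaks never enter. It does not help a patient who continues on drug, or whose value has fallen by that visit.
- **Other outputs show the case.** Under Protocol 6.5.2.1.1 a new clinically significant or symptomatic laboratory abnormality is an adverse event, so it enters the adverse event tables. SAP 8.7.2 lists all of a patient's data for any flagged liver parameter or sodium, and the interim package includes listings of clinically important values. This stands and limits the harm. It does not repair the counts: adverse event reporting depends on the investigator's judgement, and a listing gives no frequency by arm.
- **Only the shift tables are worded as extreme-value tables.** This also stands. SAP 8.7.2 does not say what the liver table counts, which is a second gap rather than a defence.

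A reader might extend the point to the ECG shift table. The documents do not support that: SAP 8.7.4 tabulates ECG interpretation at each time point, so it does not purport to show the worst reading. Nor is it a defect that the safety baseline in Protocol 8.7 "will include both scheduled and repeat (unscheduled) observations": taking the last pre-dose value is a separate definition.

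**Conclusion.** The point holds in a limited form and should be corrected. Read with SAP 8.1, the shift tables and liver-threshold table in SAP 8.7.2 will usually leave out a peak found on an unscheduled draw, and the resulting per-arm counts can only be too low. The gap is in the SAP; the protocol sentence on shift tables is not at fault. The conclusion assumes that the SAP 8.1 default is applied where no exception is written and, for the liver table, that the intention is to count patients with any value over the threshold.

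The number of patients affected cannot be computed: the documents give no rate of unscheduled draws and no rate of abnormalities. A reader might try to size the loss by asking how often an abnormality of some assumed length would span Day 42 or Day 84. That would measure the sparse schedule under invented durations, not values lost to this rule, since an episode with no extra draw is missed under any rule. Because adverse event tables and listings still show the cases, this is a weakness in the summary evidence on dose safety, not a concealment of it.

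**What to change.** In SAP 8.7.2, state that the L/N/H shift tables and the clinically important laboratory value tables use all on-treatment results, scheduled and unscheduled, as is already written for sodium. State also that the liver table counts patients with any on-treatment value over the threshold. Refer to this rule from SAP 8.9.2.5 so that the interim table follows it. Keep scheduled visits only for the by-visit summary statistics and mean changes.

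The cost is a sentence or two and minor programming; no new data are needed. One downside is that patients with more draws have more chances to cross a threshold, so the number of patients with unscheduled draws should be reported by arm beside these tables.
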